Once the individual has signed the informed consent document for the study and it has been verified that they meet all the inclusion criteria and none of the exclusion criteria, they will be considered eligible to be included in the study. In this first contact with the patient, you will fill out a first SF-36 health questionnaire.

Each patient will be assigned a numerical code consecutively as they are included in the trial. Randomization should be done in the operating room at the time prior to abdominal wall closure (optimal time for drain placement). This moment is chosen for randomization to avoid randomizing patients who ultimately require drainage due to intraoperative conditions by decision of the surgeon and not by randomization. Randomization will be performed using a spreadsheet with restricted access to participating centers through simple randomization. In order to carry out the randomization, the sheet will require filling in the initial data of the patient with which it will be verified that he meets the inclusion criteria in the study and none of the exclusion criteria. Subsequently, he will proceed to randomization and assign a number to the patient.

- **STUDY POPULATION**

- **Definition of the study population**

Patients will be recruited into the transplantation committee of the Hospital Clínico Virgen de la Arrixaca University. 365 individuals will be selected from both sexes, aged between 18 and 75 years, diagnosed with cirrhosis, liver disease, fulminant hepatitis or other indications specific to HT.

- **Inclusion criteria.**

- Patients of both sexes aged between 18 and 75 years included in the waiting list for HT by the committee of the Virgen de la Arrixaca University Hospital.
- Sign Informed Consent.

- **Exclusion criteria.**

- Having been rejected for liver transplantation by said committee.
- Age less than 18 years or greater than 75.
- Any contraindication by the main surgeon that makes the placement of an intra-abdominal drain necessary.
- Not having signed the Informed Consent.

- **Abandonment and replacement of patients.**

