- **SF-36:** Physical function, physical role, body pain, general health, vitality, social function, emotional role, mental health (on inclusion in the waiting list, one month after surgery, 4 months after surgery).

- **SUBJECT FOLLOW-UP**

As we have previously indicated, patients will be evaluated daily by the research staff during their hospital stay. Those who were discharged before day 30 post-transplant will continue to contact the researchers by phone and report any event related to the insertion point of the drain.

Calls will be made from discharge, the first 30 days every 15 days, from the month of discharge the periodicity will be monthly until 90 days from the intervention. The last follow-up call will be made on day 90.

- **SAFETY ASSESSMENT (only for medicines, food or other therapeutic procedures).**

All patients assigned to the control group (DN) will be reevaluated intraoperatively. If, for obvious clinical reasons, the placement of the drain is required, said patient will be excluded from the study (randomization will not be carried out, so it would not be included in the RCT) and the drain will be placed.

Patient safety was not impaired at any point in the study, with the intervention group (D) being the routine procedure in LT and the control group (ND) re-evaluated intraoperatively.

- **STATISTICS**

- **Data handling**

The data collection will be carried out through a Data Collection Notebook, capturing all the data in it legibly and in blue pen. Subsequently, said data will be dumped into a CRD through a spreadsheet. This sheet allows online access for the different study participants, to perform randomization and assign the patient code and to enter the data of each of the included patients. Patients will be included without personal data or identification documents, only an identification code that will be assigned to each one at the time of randomization. Once the trial is finished, all the data collected in the database will be evaluated for the writing of the final report.

All the documentation related to the study will remain stored in the Investigator's File, in the participating center, under the custody of the Principal Investigator until the end of the study. Once the study is finished, the documentation will be indexed and transferred to the general file of the center, complying with the recommendations established with respect to the Good Clinical Practice Standards.

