Access to the information of the participating subjects will be restricted to the study doctor and authorized collaborating team members. The researcher and the center will guarantee direct access to the data or source documents to the personnel authorized by the promoter (monitor, auditor), to the health authorities (Spanish Agency for Medicines and Health Products), and to the Ethical Committee for Clinical Research, when need it.

- **DATA MANAGEMENT AND RECORDS FILE**

Patient data will be collected in a CRD. The principal investigator or a sub-investigator of the center must ensure the accuracy and completeness of the data recorded and put their signature on the corresponding CRDs. These data will be exported to REDCap, which will be the platform on which all the data from the centers participating in the trial will be shared.

When the database has been considered complete and accurate, it will be closed by locking the database. The filing of all relevant documents in relation to the study will be

carried out according to the requirements of the ICH-GCP, Commission directive 2005/28 / EC of April 8, 2005, and according to the pertinent national laws.

- **DATA PROTECTION**

The data will be included in a database that must comply with Regulation 679/2016, of April 27, General Data Protection Regulation and Organic Law 3/2018, of December 5, on the Protection of Personal Data and guarantee of digital rights. Likewise, the transmission of said data will be done with the appropriate security measures in compliance with said regulation. During documentation and analysis, patients will only be identified by their individual patient code, while all subject names will be kept secret by the investigator.

- **FINANCING AND INSURANCE**

No extraordinary financing is necessary, since we will use available resources in daily clinical and surgical activity. This study would be exempt from the need to take out insurance since the patients will undergo two surgical techniques performed in routine clinical practice and do not pose an additional risk to the patient.

- **PUBLICATION POLICY**

Each researcher is free to publish data from their center. However, the collected data will be presented and published by the appropriate author according to the criteria established by the International Committee of Medical Journal Editors (ICJME). Data will be published regardless of trial results.

- **BIBLIOGRAPHY**

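### Enrolling centres draw the allocation in the same shared online spreadsheet they use for data entry, with no stated safeguard that hides upcoming assignments or makes a draw final

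*Combined protocol and SAP*

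**What the plan says.** The subsection on sampling and randomization, under Study design, sets the method: "Randomization will be performed using a spreadsheet with restricted access to participating centers through simple randomization". It places the draw in theatre: "Randomization should be done in the operating room at the time prior to abdominal wall closure". Before the draw, "the sheet will require filling in the initial data of the patient with which it will be verified that he meets the inclusion criteria" and none of the exclusion criteria. Then: "Subsequently, he will proceed to randomization and assign a number to the patient".

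Under Statistics, Data handling shows that this sheet is also the data-entry tool. Paper records come first, and then "Subsequently, said data will be dumped into a CRD through a spreadsheet". On its users it says: "This sheet allows online access for the different study participants, to perform randomization", and the same access serves for issuing codes and entering each included patient's data.

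The section on data management and the records file names REDCap as the destination of the exported data, "which will be the platform on which all the data from the centers participating in the trial will be shared". REDCap is not given a role in allocation.

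Three other places matter. The Abstract states that there is no masking. The exclusion criteria include the main surgeon's judgement that a drain is needed. Safety assessment says that patients already allocated to control are re-evaluated during the operation and excluded if a drain is required, and adds in the same sentence that such patients are not randomized. Study design instead provides for a drain within the control group when the surgeon thinks it necessary.

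**The concern.** Allocation concealment requires that whoever decides on entry cannot know the next assignment and cannot undo it once it is seen. Here the people who enrol, judge eligibility and enter data also operate the tool that allocates. The access restriction keeps outsiders away from the sheet but does not separate enrolment from allocation.

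The timing makes this important. The draw takes place at closure, when the surgeon can still declare a drain necessary and so exclude the patient. If the arm could be foreseen, or seen and then redrawn, the patients most likely to be withheld from no drain are those at highest risk of bleeding or bile leakage. Their removal would lower the no-drain complication rate, and redrawing them into the drain arm would raise the other rate. Both effects favour non-inferiority, the hypothesis under test, and later analysis could not reliably undo them.

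**Working it through.** **1. What the text covers.**

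| Safeguard | Stated? |
|---|---|
| Access limited to participating centres | Yes (randomization subsection) |
| Eligibility data entered before the draw | Yes (same subsection) |
| Eligibility decision locked before the arm is shown | No |
| Sequence prepared by someone outside enrolment | No |
| Upcoming assignments hidden from sheet users | No |
| Draw final, time-stamped and audited | No |
| Log of patients excluded in theatre | No |

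The double entry and consistency filters described under Data handling concern the database, not the draw.

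**2. The order of exclusion and allocation.** The randomization subsection puts the draw after the eligibility check, so that patients who need a drain are never randomized. The first statement in Safety assessment has patients with a control assignment being re-evaluated and excluded. Its parenthesis says that they are not randomized. Study design keeps a control patient who receives a drain within the control group. These statements cannot all describe one sequence. Exclusion before an unknown draw affects both arms alike and does not bias the comparison. Exclusion after the arm is known removes patients from one arm only.

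**3. The plan's own sample size.** Inputs from Sample size: 9% drain, 6% no drain, margin 4 points, alpha 0.05, power 80%. The distance to the margin is 0.04 + 0.03 = 0.07.

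n per arm = (0.09 × 0.91 + 0.06 × 0.94) × (1.645 + 0.842)² / 0.07² = 174.5

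This reproduces the stated 174 with a one-sided alpha of 0.05. A one-sided alpha of 0.025 gives 222. For the total, 348 × 1.05 = 365.4, against the stated 365. The allocation issue changes none of these inputs, so there is no corrected sample size.

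**4. What a bias would do (assumptions, not figures from the documents).** Take true risks exactly at the margin, 9% drain and 13% no drain, with 174 per arm.

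SE = √[(0.09 × 0.91 + 0.13 × 0.87) / 174] = 0.0335

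False non-inferiority rate = Φ(−z + b / SE), where b is the shift in the observed difference in favour of no drain and z is 1.645 or 1.960. The SE is held at its unshifted value.

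| Assumed shift b (points) | One-sided alpha 0.05 | One-sided alpha 0.025 |
|---|---|---|
| 0 | 5.0% | 2.5% |
| 0.5 | 6.7% | 3.5% |
| 1 | 8.9% | 4.8% |
| 2 | 14.7% | 8.7% |
| 3 | 22.7% | 14.4% |

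To say which row applies, one would need the share of patients diverted and their complication risk. The documents give neither.

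**The case against.** The strongest reply is that the documents do not show a defective tool. A spreadsheet can have a protected list, locked cells or a logged script, and the protocol does not say how this one works. A reader might infer that users can read the list or repeat a draw; the text supports only that nothing is said to prevent it. This stands, and it limits the finding to unspecified safeguards. It is still more than a reporting gap, because the plan places allocation in a tool shared with the people who enrol.

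The plan also has real protections. Eligibility data come before the draw, patient codes are consecutive and leave a partial trace, and simple randomization makes earlier assignments uninformative about the next. These stand as well, but none of them hides a stored list, locks the surgeon's decision or stops a second draw.

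The surgeon's exclusion is not itself a bias. The protocol times the draw so that such patients are left out beforehand, which is sound if the arm is truly unknown.

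A reader might also infer that centres can watch results accumulate by arm. Data handling grants access to randomize, assign codes and enter data; it does not say that one centre sees another's outcomes. The explicit statement about sharing all centres' data concerns REDCap, so moving allocation there would not by itself settle who sees what.

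Finally, part of the introduction and the pages between Annex 2 and Annex 5 were not available, so 'not stated' refers to the remaining text.

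**Conclusion.** The point holds as a weakness in the allocation procedure that should be corrected. Enrolling centres allocate in a shared data-entry sheet, in an unmasked trial, when the surgeon's judgement still decides eligibility, and the text describes nothing that secures concealment or a single irrevocable draw. The contradictory statements on exclusion and on drains in controls add to this, because on one literal reading exclusion depends on the arm.

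The documents do not support a claim that allocation has been or will be subverted, or any estimate of how many patients would be affected. The direction of a bias, if one arose, would be towards non-inferiority, assuming that the patients withheld from no drain are those at higher risk. Its size is unknown. The error rates above show only how sensitive a 4-point margin with 174 per arm would be to shifts of 0.5 to 3 points. The planned sample size is unaffected.

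**What to change.** Move allocation out of the shared data-entry sheet to a central concealed system. A REDCap randomization module is one option, since REDCap is already named for the data; an equivalent central service would also do. Specify in the protocol:

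- a sequence prepared by someone not involved in enrolment and hidden from all sites;
- the surgeon's eligibility decision recorded and locked before the arm is released;
- one time-stamped, audited release per patient that cannot be redrawn;
- a log of consented patients excluded in theatre, with the reason;
- who may view which centres' data on the platform.

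Reconcile the statements in Study design, the randomization subsection and Safety assessment on exclusions and drains in the control group, so that one order of events is described. Which clinical rule applies is for the investigators to decide.

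The cost is set-up work, amended wording in the randomization and Data handling sections, and system access for theatre staff at closure. The present plan already needs online access at that moment. Whether a REDCap module is available at every centre is not stated and must be checked.

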 - To evaluate the possible improvement in the quality of life of the transplanted patient derived from the absence of postsurgical drainage (SF-36).
 - Evaluate the postoperative stay in both groups.

- **STUDY DESIGN**

Unmasked European multicenter randomized clinical trial with two arms parallel to the study.

Patients who meet the inclusion criteria will be offered to participate in this study by signing an informed consent. An informed consent approved by the Research Ethics Committee of the Virgen de la Arrixaca University Hospital will be used.

Patients who give their consent for the study will be randomized to the drainage group (D) and the control group without drainage (ND) before the beginning of the abdominal wall closure.

In the drainage group (D), it will be placed on the right flank / right iliac fossa. The drain will be connected to a bag and fixed to the skin with a silk. Said drain will be placed at the level of the surgical bed.

Regarding the control group, intraoperative drainage will not be placed, except when the surgeon's discretion considers it necessary due to the high risk of bleeding, bile leakage or any other process / complication in which it may benefit from intra-abdominal drainage.

All patients, regardless of the randomization group, will receive a quality of life questionnaire (SF-36) prior to surgery that they must complete.

All patients will receive routine antibiotic prophylaxis 60 minutes before surgery, repeating the number of doses that are required according to blood loss and surgical time. Antibiotic prophylaxis will be adjusted according to the resistance protocols of each participating center.

○ **DATA COLLECT**

The following variables will be collected for each patient:

- **Recipient preoperative** variables: gender, age, pre-transplant stay, BMI, ASA, diabetes, HTN, dialysis, MELD, Child-Pugh, serology, albumin, bilirubin, INR, CRP, creatinine, ascites, SBP, prothrombin time, encephalopathy, time from SSI to HT (months), retransplantation, previous surgeries, cirrhosis etiology, indication for transplantation, sarcopenia.
- **Donor** characteristic variables: age, stay in ICU, vasoactive drugs, cultures, antibiotics, CIT, WIT, type of donation (DBD / DCD), previous immunosuppression.

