The Principal Investigator will ensure that subject identification codes are kept for at least fifteen years after the trial has been completed or discontinued.

The data of all the CRDs will be entered into a database created for this purpose and equipped with safety margins and internal coherence standards. This database will be equipped with a double entry system and filters that prevent and detect any type of inconsistency or error in it. The information will be validated through internal consistency controls, studying the missing values. The data will be verified and corrected until the

database is fully validated. Once the database is purged, the variables will be recoded generating new variables (regrouping, sums, etc.).

- **Sample size.**

The hypothesis of this study was that the risk of postoperative complications at 90 days in the ND group would not be higher than in group D. A non-inferiority configuration was selected because the omission of drain placement is advantageous in terms of relieving to patients from discomfort and a decrease in medical cost. In calculating the sample size, the risk of an early postoperative complication related to LT was assumed to be 9% in the drain group and 6% in the no-drain group according to the literature review performed. Under a 4% non-inferiority margin, an alpha error of 0.05, and a statistical power of 80%, the sample was calculated as 174 patients in each arm. Assuming a 5% dropout rate, a total of 365 patients will be recruited into this study.

- **Statistic analysis**

The subsequent statistical analysis will be performed with the SPSS v.25 software.

- **Descriptive analysis.**

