The demographic data and other baseline characteristics of the trial subjects will be described using descriptive statistical indices, for the overall number of patients and for each of the groups of patients under study. Continuous variables will be described using measures of central tendency (mean) and measures of dispersion (standard deviation). While the categorical variables will be described through absolute and relative frequency tables. The baseline characteristics shown by the groups of participants included in the study will be compared. Statistical tests will be performed depending on the nature of the variables. To study the relationships between variables, standard chi-square tests have been used in the case of qualitative variables and Pearson's correlation in the case of quantitative variables. In each situation, any association in which the p-value was less than 0.05 was considered statistically significant. The magnitude of the association between qualitative variables will be made by calculating the relative risk, and between quantitative

variables using Pearson's correlation coefficient. In this multivariate analysis, the odds ratios will be obtained with a 95% confidence interval.

- **Analysis of the main variable**

The primary efficacy criterion is the comparison of the incidence of postsurgical complications according to the Clavien-Dindo classification.

- **Secondary variables analysis**

The univariate and multivariate study of all the included variables will be carried out.

- **ETHICS**

This study will be carried out in European hospitals in accordance with current European legislation that regulates the performance of clinical trials, for which this protocol is established as a reference document for review by the Ethics Committees, as well as for the taking of practical decisions in the management of included patients by participating investigators. The study will only begin after obtaining written authorization from the Clinical Research Ethics Committee.

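### The SF-36 objective has no key score or time, no between-arm method and no multiplicity control, so up to 16 unadjusted comparisons could carry a 15–33% chance of a false benefit

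*Combined protocol and SAP*

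**What the plan says.** Under Secondary objectives, the protocol sets out "To evaluate the possible improvement in the quality of life of the transplanted patient" and attributes that improvement to the absence of a drain, with the SF-36 as the measure. Postoperative stay is the only other secondary objective. The abstract also lists quality of life as an aim, without giving a direction.

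Under Study variables, the SF-36 is listed as eight domains: "Physical function, physical role, body pain, general health, vitality, social function, emotional role, mental health". They are collected at three times: "on inclusion in the waiting list, one month after surgery, 4 months after surgery". Two of these follow surgery.

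Under Statistics, the whole plan for secondary variables is one sentence: "The univariate and multivariate study of all the included variables will be carried out". The tests are named in the descriptive-analysis paragraph: "standard chi-square tests have been used in the case of qualitative variables and Pearson's correlation in the case of quantitative variables". The same paragraph sets the threshold: "In each situation, any association in which the p-value was less than 0.05 was considered statistically significant". Its multivariate analysis is to yield odds ratios.

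No section names a leading SF-36 domain, summary score or time. None gives a testing order or an adjustment for multiplicity, and none calls the SF-36 results exploratory.

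**The concern.** The objective is directional, but nothing says which result would meet it. With eight domains, two postoperative times and a threshold applied to each association separately, a single favourable domain at a single time could be reported as a significant quality-of-life gain from omitting the drain. A reader could not tell that gain from chance, because the plan does not say which comparison was meant to count.

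The missing method widens the choice. Chi-square, a correlation coefficient and an odds ratio are not, as described, comparisons of a quantitative score between two arms. The method, as well as the domain and the time, therefore stays open until data exist.

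What is at stake is the credibility of one secondary claim. The Sample size section gives relief of discomfort as one reason for choosing a non-inferiority design, and the SF-36 is the trial's only patient-reported measure of anything like it. If non-inferiority is shown, an SF-36 result is likely to be quoted beside it.

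**Working it through.** **The plan's own figure.** The documents state no error rate, effect size or power for the SF-36. The only design calculation is for complications, with rates "assumed to be 9% in the drain group and 6% in the no-drain group", a 4% margin and 80% power. With one-sided alpha 0.05 and unpooled variance:

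(0.09 × 0.91 + 0.06 × 0.94) × (1.645 + 0.842)² / (0.04 + 0.03)² = 174.5 per arm, against 174 stated.

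348 × 1.05 = 365.4, against 365 stated. The figure reproduces, and it does not depend on the SF-36.

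**Inputs for the SF-36**
- Domains: 8 (Study variables).
- Postoperative times: 2, at one and four months (Study variables).
- Threshold: 0.05 per association, unadjusted (Descriptive analysis). Sidedness is not stated; I take it as two-sided, so 0.025 falls in the direction of benefit.
- Comparisons: 8 × 2 = 16, one per domain and time. This is an inference from the sentence on secondary variables.
- Correlations between domains and between times: not given, so I assume a range.

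**No true effect, independent tests**
- At least one significant difference in either direction: 1 − 0.95^16 = 56.0%.
- At least one false benefit for no drain: 1 − 0.975^16 = 33.3%.
- Ceiling on a false benefit under any correlation: 16 × 0.025 = 40%.

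**No true effect, correlated tests.** I used 400,000 draws of 16 normal statistics, with a common correlation between domains and another between the two times. Each cell gives the chance of a false benefit, then the chance of a false difference in either direction.

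| Between domains | Times 0 | Times 0.3 | Times 0.5 | Times 0.7 |
|---|---|---|---|---|
| 0.3 | 28.1% / 50.9% | 26.7% / 50.0% | 25.3% / 48.2% | 23.4% / 45.3% |
| 0.5 | 23.5% / 43.8% | 22.2% / 42.9% | 21.1% / 41.2% | 19.4% / 38.5% |
| 0.7 | 18.2% / 34.5% | 17.3% / 33.9% | 16.2% / 32.3% | 14.9% / 29.8% |

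**Against nominal.** One named test at two-sided 0.05 gives a false benefit with probability 2.5%. The ratio runs from 14.9/2.5 = 6 to 33.3/2.5 = 13.

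**Under a correction.** Bonferroni over 16 tests uses 0.05/16 = 0.003125 each. The chance of a false benefit is then about 2.5% if the tests are independent and 1.4–2.4% over the correlations in the table.

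**The case against.** The strongest reply is that the 16 tests are not in the plan. The threshold sentence stands in the descriptive paragraph, after two methods that do not compare mean scores between arms, and no SF-36 comparison by domain or by time is laid out. That is correct, so the 16 must be called an inference. It does not remove the problem. The threshold is worded to cover every situation, it is the only rule given for associations, and the SF-36 domains are among the variables to be studied. An unspecified analysis leaves more room for selection than a specified one.

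A second reply is that this is a secondary outcome, and that many trials report such outcomes unadjusted as supportive. This stands as to weight. But here the results are not labelled supportive or exploratory, and the rule would call them significant.

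Three stronger readings go beyond the documents:
- A reader might take 56% as the chance of a false quality-of-life benefit and call one likely. That figure counts differences in either direction, including those favouring the drain. For benefit alone the chance is below one half under any correlation.
- A reader might infer that the SF-36 supports the 4% margin. The Sample size section offers reduced discomfort as a reason for the non-inferiority design. It does not offer it as a reason for the size of the margin, or as a hypothesis the SF-36 must confirm.
- A reader might extend the point to the baseline comparisons under the same threshold. Those carry no treatment claim and do not bear on quality of life.

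**Conclusion.** The concern holds as a gap in prespecification for one secondary objective. If each domain is compared between arms at each postoperative time, the chance of at least one false benefit for no drain is about 33% under independence and about 15–28% at the assumed correlations. That is 6 to 13 times the 2.5% of a single named test. For a claim of any difference, in either direction, the chance is about 30–56%.

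These figures rest on four assumptions: 16 comparisons, one analysis for each, two-sided tests, and correlations that the documents do not supply. Running both univariate and multivariate versions could add to the count. The trial is unmasked, which may bias self-reported scores; that is a separate matter and is not in these numbers.

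The margin, the sample size and the primary conclusion are unaffected. This is a worthwhile, cheap improvement; the documents do not support calling it a flaw in the main result.

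**What to change.** In the Statistics section, under Secondary variables analysis, name one SF-36 score at one postoperative time as the single test of the quality-of-life objective, at two-sided 0.05. The sponsor should choose it before any data are seen. State the between-arm comparison, for example a difference in means adjusted for the baseline score, since a pre-transplant SF-36 is already collected. Report the other 15 comparisons as exploratory estimates with 95% intervals and no claim of significance. Limit the general p < 0.05 sentence so that it does not reach them.

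This takes a few sentences and no extra patients, visits or data. The downside is that an effect confined to a domain or time that was not named could not be claimed as confirmed.
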